7.3 Trial Steering Committee

The Trial Steering Committee (TSC) will approve the main study protocol and any amendments, monitor, and supervise the trial towards its interim and overall objectives, review relevant information from other sources, consider the recommendations of the Data and Safety Monitoring Board (DSMB), and resolve problems brought by the trial coordinating centre. The TSC will meet every 6 months, with those not in the UK joining by teleconference.

Chair: [name], College of Medicine, Blantyre, Malawi

Members:

- [name], President, Uganda Paediatric Association, Kampala
- [name], Chief of Health, UNICEF, New York
- [name], International Network in Kangaroo Mother Care, WHO Collaborating Centre for Maternal & Child Health (retired), Trieste, Italy

8. Safety and Monitoring

Safety oversight will be the responsibility of the investigators led by the PI, and the DSMB.

8.1 Monitoring of Study Participants

The minimum clinical monitoring schedule is shown in Table 2. In order to assess the validity of axillary temperature measurements, temperature will be continuously recorded during the first 24h post-randomisation using Grant Instruments YL-T11 temperature loggers in approximately 5% of neonates in each arm of the trial.

Table 2. Clinical Monitoring Schedule

Every 6 hours in unstable neonates in both intervention and control arms		Daily in stable neonates in both intervention and control arms	
Measurement	Method	Measurement	Method
Heart rate (continuous monitoring during first 72h post-randomisation)	Pulse oximeter	Heart rate	Pulse oximeter
Axillary temperature	Clinical thermometer	Axillary temperature	Clinical thermometer
Respiratory rate	Observe and count breaths for 1 minute	Respiratory rate	Observe and count breaths for 1 minute
Oxygen saturation (continuous monitoring during first 72h postrandomisation)	Pulse oximeter	Oxygen saturation	Pulse oximeter
Respiratory distress	Observe for chest indrawing, nasal flaring, and grunting	Respiratory distress	Observe for chest indrawing, nasal flaring, and grunting
Blood glucose (every 6h during first 24h, then daily while advancing enteral feeds)	Glucometer and blood glucose test strips		

Alarms on pulse oximeters will be set to detect bradycardia (HR <100 bpm) or hypoxaemia (SpO₂ <88%), so these neonates can be assessed by a study nurse and followed more closely. Clinically significant episodes of apnoea and/or bradycardia, which necessitate initiation of bag-mask ventilation, will be recorded as serious adverse events (SAE). See Section 6.1.3 for further details on evaluations to be completed in the event of clinical deterioration.

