Appendix F: Investigators' CVs.....	64

List of Abbreviations

AE	Adverse event
bpm	Beats per minute
CI	Confidence interval
CONSORT	Consolidated Standards of Reporting Trials
CPAP	Continuous positive airway pressure
cUS	Cranial ultrasound
d	Day(s)
DSMB	Data and Safety Monitoring Board
eCRF	Electronic case report form
EH	Entebbe Regional Referral Hospital
FGD	Focus group discussion
g	Grams
GCP	Good Clinical Practice
HR	Heart rate
h	Hour(s)
IH	Iganga District Hospital
ID	Identification
IDI	In-depth interview
IRB	Institutional Review Board
ICH	International Conference on Harmonisation
IV	Intravenous
IVH	Intraventricular haemorrhage
JH	Jinja Regional Referral Hospital
KNRH	Kawempe National Referral Hospital
LBW	Low birthweight
LMIC	Low- and middle-income countries
LSHTM	London School of Hygiene and Tropical Medicine
KMC	Kangaroo mother care
MH	Masaka Regional Referral Hospital

MIRI	Maternal Infant Responsiveness Instrument
MRC/UVRI	Medical Research Council/Uganda Virus Research Institute Uganda Research Unit in Entebbe
OMWaNA	‘Operationalising kangaroo Mother care before stabilisation amongst low birth Weight neonates in Africa’
PI	Principal Investigator
PIS	Participant information sheet
PSBI	Possible serious bacterial infection
RCT	Randomised controlled trial
RR	Relative risk
SAE	Serious adverse event
SGA	Small for gestational age
SOP	Standard operating procedure
SpO ₂	Oxygen saturation measured by pulse oximetry
SSC	Skin-to-skin contact
TMF	Trial Master File
TSC	Trial Steering Committee
UgSh	Ugandan Shillings
WCI	Women’s Capabilities Index
WHO	World Health Organization

Definitions

Adverse event:	Any untoward medical occurrence in a patient or clinical investigation subject administered an experimental therapy, which does not necessarily have to have a causal relationship with this therapy (1)
APGAR score:	System for assessing newborns and response to neonatal resuscitation at the time of delivery; includes 5 components: 1) colour, 2) heart rate, 3) reflexes, 4) muscle tone, 5) respiration; each component is scored 0 to 2 at 1 and 5 minutes post-birth, and at 5-minute intervals thereafter up to 20 minutes for infants scoring <7 (2)
Apnoea:	No spontaneous breathing for 20 seconds, or less than 20 seconds and accompanied by colour change, oxygen desaturation ($\text{SpO}_2 < 88\%$), or bradycardia (HR <100 bpm)

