1.4.2 Secondary outcomes

- Prevalence of hypothermia at 24 hours post-randomisation
- Mean duration of hospital admission (days and hours)
- Mean time from intervention/control procedures starting to exclusive breastmilk feeding (days and hours)
- Mortality within 28 days
- Time from intervention/control procedures starting to clinical stabilisation (days and hours)
- Time from intervention/control procedures starting to death (days and hours)
- Frequency of readmission
- Mean daily weight gain (g/day) at 28 days
- Infant-caregiver attachment at 28 days
- Women's well-being at 28 days

2. Background

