3.2.5 Clinical Stability Criteria

Neonates will be considered stable when the following criteria have been met for a continuous period of at least 24h [criteria consistent with the WHO I-KMC trial (61)]:

- (i) Breathing spontaneously with $\text{SpO}_2 >90\%$ in room air
- (ii) No need for supplemental oxygen or CPAP
- (iii) Respiratory rate 40 to <60 breaths per minute
- (iv) No apnoea
- (v) HR 80 to <180 beats per minute
- (vi) Axillary temperature 36.0 to 37.4 degrees Celsius
- (vii) No need for IV fluids

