6.1 Clinical Evaluations

6.1.1 Evaluations during first 24 hours

All participants will receive continuous monitoring and recording of HR and SpO₂, using a pulse oximeter, for 72h post-randomisation. Continuous monitoring will continue until participants no longer require any form of respiratory support.

Axillary temperature and respiratory rate will be manually measured every 6h for the first 24h. All participants will be evaluated at least once by a study paediatrician or medical officer during the first 24h post-randomisation. Blood glucose will be measured every 6h, unless <2.6 mmol/l in which case it will be measured hourly until 2 or more consecutive readings are in normal range (2.6 – 6.9 mmol/L).

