14.3 Evaluation of risks and benefits

14.3.1 Potential risks or benefits of standard care in Uganda

Incubators are the standard alternative to KMC for maintaining normothermia in preterm and low birthweight neonates. In resource-limited facilities such as the four trial hospitals, it is common for several neonates to share one incubator or radiant heater. In this trial, neonates randomised to the control group will receive standard care. Risks associated with standard care with an incubator or radiant heater include hypothermia (40,76); hyperthermia (77); nosocomial infections, related to lack of effective cleaning standards (78–80); and cross-infection from other neonates when incubators are shared, a common practice in low-resource facilities. Failure of incubators/heaters to properly regulate temperature may be related to malfunction (e.g., over- or under-heating) (77,80–83), loss of electrical supply (51), ignorance of how to regulate set-points (77), as well as environmental factors (81). In lowresource hospitals, where there may be few nurses and doctors available, neonates nursed in incubators/heaters may not be monitored well, and illness or serious events (e.g., apnoea) may not be detected in time. Such events may be detected more rapidly when neonates are in the KMC position with their mother (or another caregiver). Further, due to high purchase cost and poor routine maintenance practices, hospitals in low-resource settings commonly face shortages of functional incubators (50–52,84).

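### After 72 h and off respiratory support, the no-apnoea condition for clinical stabilisation rests on incidental observation, which may differ between the arms

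*Protocol*

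**What the plan says.** Section 1.4.2 lists as a secondary outcome "Time from intervention/control procedures starting to clinical stabilisation (days and hours". Section 3.2.5 defines the event: "Neonates will be considered stable when the following criteria have been met for a continuous period of at least 24h". Seven criteria follow. Criterion (iv) is the absence of apnoea, and another is "ii) No need for supplemental oxygen or CPAP". The Definitions describe apnoea as "No spontaneous breathing for 20 seconds, or less than 20 seconds and accompanied by colour change", desaturation below 88% or a heart rate below 100.

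On observation, section 6.1.1 gives continuous heart rate and SpO2 recording "for 72h post-randomisation. Continuous monitoring will continue until participants no longer require any form of respiratory support". Table 2 in section 8.1 mentions continuous monitoring for the first 72 h only. Section 6.1.2 and Table 2 then ask for heart rate, SpO2, respiratory rate and temperature every 6 h until the baby is stable, with respiratory rate counted over one minute. Table 2 has no apnoea row, and the daily data list in 6.1.2 has no apnoea item.

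Apnoea is picked up by two routes. Section 8.1 says: "Clinically significant episodes of apnoea and/or bradycardia, which necessitate initiation of bag-mask ventilation, will be recorded as serious adverse events (SAE". Section 6.1.3 with Figure 2a makes new or persistent apnoea a sign that unit staff report. An examination and safety documentation follow, and the signs are looked for again on daily rounds.

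Section 14.3.1 says of illness and serious events, apnoea among them: "Such events may be detected more rapidly when neonates are in the KMC position with their mother (or another caregiver".

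**The concern.** An apnoea that is seen restarts the 24 h clock, and one that is missed does not. The measured time to stabilisation therefore depends on detection as well as on the baby. Section 5.7.1 asks for skin-to-skin contact 18 h a day in the intervention arm. Section 5.7.2 allows none in the control arm until stability. If the person holding the baby notices more short apnoeas than staff passing an incubator, the KMC arm will appear to stabilise later with no true difference between arms. Care cannot be blinded, so nothing in the design removes this. An analysis plan cannot recover observations that were never collected.

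**Working it through.** The protocol states no figure on this point, so there is none to reproduce. The check has three steps.

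**1. Can continuous monitoring cover the qualifying 24 h?** A baby on oxygen or CPAP fails criterion (ii), so the 24 h window can start only once support has ended. Within 72 h of randomisation, both arms have continuous, alarmed heart rate and SpO2. That is good cover, although oximetry does not measure breathing pauses directly. After 72 h, section 6.1.1 requires continuous monitoring only while support is needed, and Table 2 does not mention it at all. On either reading it may lapse just when a late window can begin.

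**2. What do the scheduled checks see?**
- Four one-minute counts in 24 h cover 4/1440 = 0.28% of the window. Counting any overlap with a 20-second apnoea gives 4 × 80/86,400 = 0.37%.
- The chance that at least one of k evenly and independently spread apnoeas is seen is 1 − (1 − c)^k. With an assumed k = 5, this is 1 − (1 − 0.0028)^5 = 1.4%, or 1.8% with overlap.
- Caregiver contact covers 4.5/24 = 18.8% to 9.7/24 = 40.4% of the day at the feasibility-study medians (section 2.4), and 18/24 = 75% at the target. If every apnoea during contact were noticed, which is an upper bound, the chance of seeing at least one of five is 65%, 92% and 99.9% respectively.

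**3. How large could a false difference be?** This is an illustration with no true effect, and every input is an assumption. The other criteria are met at a lognormal time (median 6 days, SD of log 0.4). The apnoea rate at day t is r0 × exp(−0.25t), a fall of about 22% a day. The baby is stable after the first day with no detected apnoea. There are 690 survivors per arm.

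| Babies with apnoea | r0 per day | Detection, KMC v control | False KMC delay (days) | z |
|---|---|---|---|---|
| All | 3 | 50% v 10% | about 0.3 | about 2 |
| All | 6 | 50% v 10% | 0.6 to 0.7 | 4.4 to 5.0 |
| All | 3 | 30% v 20% | about 0.08 | about 0.7 |
| All | 6 | 30% v 20% | 0.15 to 0.18 | 1.2 to 1.4 |
| 30% | 3 | 50% v 10% | about 0.1 | about 0.5 |
| 30% | 6 | 50% v 10% | about 0.2 | about 1.5 |

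Ranges reflect separate runs and codings of the same model. The mildest combination (30% of babies, r0 = 3, 30% v 20%) gives about 0.01 days. The standard error of the difference is about 0.70/5.0 = 0.14 days, so a false delay needs about 1.96 × 0.14 = 0.27 days to look significant by itself. Counting in whole days is coarse: restarting the 24 h clock at the time of each detected apnoea roughly halves the first two rows, to 0.14 and 0.30 days.

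**The case against.** The case on the other side has real force.

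- **Recording is wider than the bag-mask rule.** A reader might infer from section 8.1 that only apnoea needing bag-mask ventilation is recorded. Section 6.1.3 and Figure 2a contradict this: other apnoea leads to a report, an examination, documentation and reassessment on daily rounds. This stands. Those routes are event-driven or once daily, however, and do not establish 24 apnoea-free hours.
- **Oximetry does not simply stop.** A reader might infer from Table 2 that it ends at 72 h. Section 6.1.1 extends continuous monitoring while support is needed, and 6-hourly oximeter checks go on until stability. The gap is confined to babies past 72 h and off support.
- **Section 14.3.1 is cautious background.** A reader might take it as showing that KMC caregivers see more apnoea. It says only that events may be detected sooner, in a passage about poorly staffed units, and section 7.2 adds nurses, a medical officer and oximeters at each site. It makes a difference between arms plausible without establishing one.
- **The eCRF is not shown.** Appendix D appears by title only, and Table 2 describes itself as a minimum schedule. An apnoea field may already exist.
- **The larger illustrations are extreme.** Detection of 50% exceeds the 19% to 40% of the day that feasibility-study contact covered. Apnoea in every baby is unlikely when eligibility includes babies up to 2000 g who receive only IV fluids or therapeutic antibiotics.
- **Dropping apnoea from the definition has a cost.** Section 3.2.5 aligns the definition with the I-KMC trial, which argues against replacing it.

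What remains is that the protocol does not say how criterion (iv) is to be established in the same way in both arms after 72 h.

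**Conclusion.** The concern holds in a limited form. For windows that run past 72 h off respiratory support, the required observations cannot show 24 h without apnoea, and the criterion falls back on incidental observation. Whether detection differs by arm is a plausible inference from sections 5.7.1, 5.7.2 and 14.3.1, and the documents do not measure it. If KMC caregivers notice more, the bias runs against KMC, so this route would not create a false benefit on this outcome.

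The size is unknown. Under the assumptions above it runs from about 0.01 to about 0.7 days (0.7 × 24 = about 17 h), and it is small whenever detection is similar in the arms or apnoea is confined to a minority of babies. The documents do not support saying that the outcome is biased by a known amount or that the result would be overturned. One secondary outcome is affected. The primary mortality outcome is not.

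**What to change.** 1. Keep the seven-criterion, I-KMC-consistent definition as the main outcome, and leave the bedside stability rule unchanged.
2. Pre-specify a sensitivity derivation of time to stabilisation from the six other criteria, which are measured on the same schedule in both arms. Removing a criterion can only bring the time forward, so the six-criterion time falls while checks are still 6-hourly. Two limits should be stated. The spot checks also only sample the 24 h, though equally in both arms. A detected apnoea that leads to renewed support would still delay the six-criterion time.
3. Unless the eCRF already does so, record at each existing check in both arms whether apnoea occurred since the last check and how it was detected (alarm, staff or caregiver). Report this by arm. Because it counts caregiver sightings, the item does not remove differential detection, but it makes it visible.
4. Reconcile section 6.1.1 with Table 2 on how long continuous oximetry runs.

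The cost is one eCRF item and one extra derivation. If the two versions agree, the secondary result does not hinge on the apnoea criterion. If they differ, the detection data help the reader judge whether ascertainment is the reason.

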8.2 Adverse Events & Assessment of Causality

Adverse event (AE) terminology is outlined in Table 3. Guidelines for assessing the relationship of the intervention to the SAE are outlined in Table 4.

Table 3. Serious Adverse Events Terminology

Term	Definition
Serious Adverse Event (SAE)	A serious adverse event is any untoward medical occurrence that: 
 • results in death • is life-threatening • requires prolongation of existing hospitalisation • results in persistent or significant disability/incapacity • requires intervention to prevent permanent impairment or damage
Suspected and Unexpected Serious Adverse Reaction (SUSAR)	These are the reactions that are serious (as defined above) but not expected AND considered to be related to the intervention. This definition captures the important events that are attributed to the intervention but do not follow known pattern of response.

Table 4. Guidelines for assessing the relationship of an intervention to an Adverse event

0	No Relationship	No temporal relationship to intervention and alternate aetiology (clinical state, environmental or other interventions); and does not follow known pattern of response to intervention
1	Unlikely	Unlikely temporal relationship to intervention and alternate aetiology likely (clinical state, environmental or other interventions) and does not follow known typical or plausible pattern of response to intervention.
2	Possible	Reasonable temporal relationship to intervention; or event not readily produced by clinical state, environmental or other interventions; or similar pattern of response to that seen with other interventions
3	Probable	Reasonable temporal relationship to intervention; and event not readily produced by clinical state, environment, or other interventions or known pattern of response seen with other interventions
4	Definite	Reasonable temporal relationship to intervention; and event not readily produced by clinical state, environment, or other interventions; and known pattern of response seen with other interventions

8.3 Emergency Procedures

In the event of an abnormal clinical or laboratory finding by study staff, the site paediatrician (or medical officer if paediatrician is not present) will direct management in accordance with standardised clinical guidelines. The site paediatrician or medical officer will then complete the appropriate safety monitoring documentation. See Section 6.1.3 for further details on evaluations to be completed in the event of clinical deterioration.

Providers (medical research officers and nurses) will inform the relevant site paediatrician/coinvestigator of any serious adverse event (SAE) or death occurring from the time of randomisation until the date of hospital discharge within 24 hours. The site co-investigators will notify the Trial Coordinator, who will ensure appropriate reporting procedures are followed (see Section 8.6 for further details).

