Kangaroo mother care:	Package of care that consists of prolonged skin-to-skin contact between neonate and caregiver, usually the mother; promotion of exclusive breast milk feeding; early hospital discharge; and adequate support and close follow-up at home (3) 
 Continuous KMC: Skin-to-skin contact between baby and caregiver for at least 18h/day Intermittent KMC: Skin-to-skin contact between baby and caregiver for periodic times of at least 1h duration per session
Low birthweight:	Birthweight <2500g; can be sub-categorised as follows (4): 
 Very low birthweight: birthweight <1500g Extremely low birthweight: birthweight <1000g
Neonatal mortality rate:	Number of neonates dying before reaching 28 days of age, per 1,000 live births in a year (5)
Neonatal period:	First 28 days post-birth; can be sub-categorised as follows (6): 
 Early neonatal period: 0-6 days post-birth Late neonatal period: 7-28 days post-birth
Preterm:	Birth at <37 completed weeks gestation; can be sub-categorised as follows (7): 
 Extremely preterm: birth at <28 completed weeks Very preterm: birth at 28 to <32 completed weeks Moderate to late preterm: 32 to <37 completed weeks
Serious adverse	Any untoward medical occurrence which: (1)

event:

- a) Results in death
- b) Is life threatening
- c) Requires prolongation of hospitalisation
- d) Results in persistent or significant disability/incapacity
- e) Requires intervention to prevent permanent impairment or damage

INCLUSION CRITERIA

Indication for KMC “uncertain” according to WHO guideline concerning clinical stability (8):

Pragmatically defined as receiving ≥ 1 of the following therapies:

- Supplemental oxygen: oxygen from cylinder, compressor or wall, which is delivered via nasal cannula, mask, or tent
- Continuous positive airway pressure (CPAP): method of maintaining low pressure distension of lungs during inspiration and expiration when infant is breathing spontaneously (9)
- Intravenous (IV) fluids: solution, typically containing dextrose and/or electrolytes, that is delivered directly to veins; indicated for neonates unable to take adequate enteral feeds
- Therapeutic antibiotics: antibiotics given only for presumed or confirmed infection (not empirically/prophylactically)
- Phenobarbital: medication used to treat neonatal seizures

EXCLUSION CRITERIA

Severely lifethreatening clinical instability:

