2.1 Kangaroo Mother Care to Improve Neonatal Survival

Each year, 15 million babies are born preterm (<37 completed weeks gestation) and 1 million deaths occur as a direct result of complications of preterm birth (16,17,25). Sub-Saharan Africa and South Asia account for three-quarters of the 2.6 million neonatal deaths that occur annually, and preterm birth is the leading cause of these deaths (15). Progress in preventing preterm birth has been limited, but major reductions in mortality could be achieved by improving care in low-resource settings (16,17,26,27). In such settings, 50% of neonates born at 32 to 34 weeks gestation, a time when nearly all should survive, die because newborn special care is not available (17,22). KMC is a package of care, which consists of: early, continuous, and prolonged skin-to-skin contact (SSC), usually with the mother; promotion of exclusive breast milk feeding; early hospital discharge; and adequate support and close follow-up at home (3). The most recent Cochrane review and a meta-analysis demonstrated that KMC among *stable* neonates ≤ 2000 g is associated with decreased mortality (RR 0.60-0.64) (20,21), sepsis (RR 0.35-0.53) (20,21), hypothermia (RR 0.22-0.28) (20,21), hypoglycaemia (RR 0.12) (21), and length of stay (mean difference -1.61 days) (20) compared to conventional care. WHO guidelines recommend KMC for “routine care of newborns weighing ≤ 2000 grams (g)... initiated as soon as newborns are clinically *stable*” (8), where stability has been defined as vital functions (breathing, circulation) not requiring “continuous medical support and monitoring,” and not being “subject to rapid and unexpected deterioration” (5).

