Finding 2: Monitoring and provision of concurrent care therapies was feasible in the KMC position: To demonstrate the feasibility of monitoring and providing care therapies (oxygen, IV fluids, etc.) in the KMC position, we enrolled a sample of 10 neonates meeting proposed trial eligibility criteria between July and December 2016. Gestational age was determined by Ballard examination (57). Mothers were counselled to provide KMC ≥ 18 h per day. During interruptions when mothers carried out activities like bathing, a family member was encouraged to provide KMC. If none was available, the neonate was placed in an incubator until the mother returned. Neonates were otherwise managed according to unit guidelines. All neonates received continuous monitoring of SpO₂ and HR.

Among the 10 neonates enrolled, median birthweight was 1310g [interquartile range (IQR) 820-1600g], median gestational age was 28 weeks (IQR 26-31 weeks), and median length of stay was 10 days (IQR 9-14 days). Eight neonates were discharged home and two died. Both neonates that died were extremely premature (26-27 weeks) and extremely LBW (700-750g), thus at very high risk of death, particularly in a low-resource setting given the lack of ventilatory support and other intensive care usually required for survival at this gestational age. The median duration of individual KMC episodes ranged from 115 to 134 minutes, and the median daily duration ranged from 4.5 to 9.7 hours, with a slight upward trend over time. Two neonates received the target duration of 18 hours of KMC on day 1 (18.1 and 21.6 hours) and one neonate received the target duration on day 5 (18.3 hours) (see Section 17 for discussion about KMC compliance). The mean number of care therapies received ranged from 3.7 to 4.1 per day across the first 14 days, and the number of therapies a neonate was receiving did not affect the daily duration of KMC. Continuous SpO₂ monitoring was conducted throughout the enrolment period for all participants, and providers did not report any problems with monitoring or care provision.

Finding 3: KMC (prior to stabilisation) and randomisation were acceptable to parents and providers:

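### SAE notification stops at hospital discharge, a time point KMC may shift, and readmission is not an SAE, although follow-up runs to day 28-30

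*Protocol*

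**What the plan says.** - **Notification window.** Section 8.3 covers SAEs and deaths "occurring from the time of randomisation until the date of hospital discharge within 24 hours". Staff notify the site paediatrician, and the report then passes to the trial coordinator.
- **Where SAEs are looked for.** Identifying SAEs is an item of the daily review in 6.1.2, which runs from 24 hours to discharge. The procedures for the day 28-30 visit (6.1.5) contain no SAE item.
- **Definition.** Table 3 in 8.2 includes an event that "requires prolongation of existing hospitalisation", and the Definitions say "Requires prolongation of hospitalisation". Neither lists a new admission.
- **Follow-up and outcomes.** Section 5.8 follows all participants to day 28-30 and records vital status and readmission. Section 1.4.2 lists 28-day mortality, duration of admission and "Frequency of readmission" as secondary outcomes.
- **KMC and length of stay.** Section 2.1 describes KMC as including "early hospital discharge; and adequate support and close follow-up at home" and cites, for stable neonates, a reduction in "length of stay (mean difference -1.61 days) (20) compared to conventional care".
- **Other reporting.** Section 8.6 says SAE forms draw on routine outcome data. It requires a 48-hour report to the ethics committees for unexpected, possibly related events, but exempts anything already listed as a primary or secondary outcome.
- **End of trial.** Section 13 declares the end of trial once all patients have reached discharge or death, not the day 28-30 visit.

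**The concern.** The length of the SAE window is fixed by an event after randomisation that the intervention may influence. If one arm goes home sooner, its SAEs are counted for less time, and the counts can differ with no difference in risk. The DSMB receives SAE summaries under 8.6, and the sponsor and ethics committees receive SAEs in annual reports.

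The second problem is coverage. KMC is encouraged at home after discharge (3.2.3, 5.8), yet SAE notification stops when the baby leaves. A baby who is sent home and readmitted ill does not become an SAE on that ground alone.

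**Working it through.** **1. Routes for an event after discharge**

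| Event after discharge | 8.3 (24 hours) | 8.6 (48 hours) | Collected elsewhere |
|---|---|---|---|
| Death by day 28 | Window closed | Exempt, listed outcome | Vital status at day 7 contact or day 28-30; cause-of-death review (8.5) |
| Readmission | Window closed; not an SAE by itself | Exempt, listed outcome | Day 7 contact or day 28-30 |
| Non-fatal SAE, no readmission, unexpected and possibly related | Window closed | Yes, if investigators become aware | No scheduled item |
| Any other non-fatal SAE, no readmission | Window closed | No | No scheduled item |

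The day 7 contact applies only to babies discharged before day 7. Section 5.8 describes it for KNRH, JH, IH and MH; EH is not listed.

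**2. How far the window could move SAE counts**

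The protocol gives no figure for this, so there is none to reproduce. The inputs are:
- Control stay L = 9, 10 or 14 days. This is an assumption, borrowed from the median of 10 days and interquartile range of 9-14 in the feasibility sample (2.4), which was 10 neonates, all given KMC.
- KMC stay = L − 1.61 days. This is also an assumption, because the 1.61 days comes from stable neonates (2.1).
- The same true SAE risk in both arms.

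Under constant daily risk, the captured ratio KMC/control = (L − 1.61)/L. For L = 10: 8.39/10 = 0.839.

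Under risk that declines exponentially with half-life h, put λ = ln 2/h. The ratio is then (1 − e^(−λ(L−1.61)))/(1 − e^(−λL)). For L = 10 and h = 5: λ = 0.1386, and 0.6875/0.7500 = 0.917.

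| L (days) | KMC stay | Constant risk | h = 10 | h = 5 | h = 3 | h = 2 | h = 1 |
|---|---|---|---|---|---|---|---|
| 9 | 7.39 | 0.821 | 0.864 | 0.899 | 0.936 | 0.965 | 0.996 |
| 10 | 8.39 | 0.839 | 0.882 | 0.917 | 0.950 | 0.976 | 0.998 |
| 14 | 12.39 | 0.885 | 0.928 | 0.958 | 0.982 | 0.994 | 1.000 |

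The half-lives are assumptions chosen to span early to late risk.

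**3. Share of follow-up covered**

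At L = 10 the notification window covers 10/28 = 36% of a 28-day period in control and 8.39/28 = 30% under KMC.

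**4. After the fix**

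With one fixed window in both arms, the ratio under no true difference is 1.00 whatever the pattern of risk. It is already 1.00 for mortality to day 7 and day 28 and for readmission, because discharge does not bound their ascertainment.

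**The case against.** The strongest reply is that 8.3 governs only how quickly ward staff tell the site paediatrician. SAE reporting proper is in 8.6, which has no discharge cut-off and draws on routine outcome data. That is fair as far as it goes. But 8.6 does not say that post-discharge events enter the SAE summaries, and no scheduled SAE item exists after discharge, so sites could reasonably apply 8.3 as the limit.

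Three stronger readings are tempting, and the documents do not support them:

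- **A reader might infer that the whole safety comparison is tilted towards KMC.** It is not. Section 10.2 specifies no between-arm SAE comparison, and the harms it does compare, death and readmission, are ascertained over fixed periods.
- **A reader might infer that late harm surfaces only at the end of the study.** Sections 8.8 and 8.9 give the DSMB regular monitoring of, and access to, all data, and it can ask for extra analyses. The committee in 8.5 reviews all deaths during the trial.
- **A reader might combine the feasibility median and the 1.61 days into one percentage of missed SAEs.** That needs constant daily risk and a stay difference carried over from stable neonates. The protocol points to early risk: section 18 reports that 66% of deaths in the Ethiopian trial fell within 12 hours of birth. Only a range is defensible.

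The direction is also open. Discharge follows newborn-unit criteria with no arm-specific rule (6.1.4), and controls may move to KMC once stable (3.2.4). If KMC improves survival, fewer stays are cut short by death, so mean inpatient time could be longer in the KMC arm.

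Finally, handling readmission as an outcome rather than an SAE is a legitimate choice, and a serious readmission may meet another SAE criterion. The protocol should then state that choice.

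**Conclusion.** The point stands in a limited form. The protocol ends SAE and death notification at discharge, looks for SAEs by schedule only in hospital, and leaves new hospitalisation out of the SAE definition, while following participants to day 28-30. SAE counts are therefore taken over a window that allocation may change.

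Under no true difference, the KMC/control ratio of captured SAEs could run from about 1.0, if risk is concentrated in the first days, down to 0.82-0.89 under constant risk. This rests on a control stay of 9 to 14 days and a KMC stay 1.61 days shorter, neither of which is established for this population.

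The coverage gap does not depend on those assumptions. Deaths and readmissions after discharge reach the DSMB through outcome data, with no notification route of their own. Non-fatal SAEs after discharge without readmission have no clear route, apart from the narrow 48-hour report. The primary analysis is not affected.

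**What to change.** 1. In 8.3, set one SAE period for both arms, from randomisation to the day 28-30 visit, with notification within 24 hours of staff becoming aware of the event.
2. Add an SAE item to the day 28-30 visit (6.1.5) and to the existing day 7 contacts (5.8), and state which day 7 arrangement applies at EH.
3. Add new hospitalisation, including readmission, to the SAE definition in the Definitions and in Table 3.
4. Align 8.6 with this period, stating how post-discharge deaths and readmissions enter the SAE summaries sent to the DSMB. Align the end-of-trial definition in section 13 as well.
5. Summarise SAEs by arm over this fixed window.

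The cost is small: wording changes and some additional SAE forms, mainly for readmissions. The contacts already take place and already collect vital status and readmission. For a baby discharged between day 7 and day 28, the next scheduled contact remains day 28-30. Earlier notice would depend on families using the contact numbers given at discharge.
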